1 OVERALL INFORMATION AND BACKGROUND

Agalsidase beta is a recombinant form of human α -galactosidase A and is obtained by recombinant DNA technology from a cell line culture from Chinese hamster ovary (CHO). The amino acid sequence of the recombinant form, as well as the nucleotide sequence that encoded it, are identical to those of the natural form of α -galactosidase A. ATC Code: A16ABO4.

1.1.1 Fabry Disease and Enzyme Replacement Therapy

Fabry disease is a rare lysosomal disease, associated with the X chromosome and caused by mutations in the gene encoding the α -galactosidase A enzyme. Decreased enzyme activity results in a progressive lysosomal accumulation of glycosphingolipids, mainly globotriaosylceramide (GL-3) in several tissues, including vascular endothelial cells, neurons, myocytes, and renal cells. This accumulation leads to cellular dysfunction, tissue remodeling, fibrosis, and ultimately, organ failure such as heart failure or stroke.

The severity of manifestations varies depending on the remaining enzyme activity of α -galactosidase A.

Fabry disease is diagnosed by decreased α -galactosidase A activity in plasma leukocytes or dermal fibroblast culture. Urine or plasma GL-3 concentrations are used as a biomarker for diagnosis and monitoring.

Plasma globotriaosylsphingosine (lyso-GL-3) concentrations have also been shown to be used as a diagnostic marker. This is because lyso-GL-3 level has shown to be increased in patients who have not shown increased GL-3 level.

Treatment with agalsidase beta is indicated as long-term enzyme replacement therapy in patients with a confirmed diagnosis of Fabry disease and may be used in adults, adolescents, and children ≥ 8 years of age.

Currently, three therapies are approved worldwide: agalsidase α (Replagal by Shire and Agalsidase Beta BS by Amicus) and agalsidase β (Fabrazyme® by Sanofi-Genzyme or JR-051 by JCR Pharmaceuticals). Treatment with these drugs decreases GL-3 accumulation in the kidneys, heart, and epithelium. It also reduces pain and maintains renal function.

1.1.2 Mechanism of Action

The rationale for the enzyme replacement therapy is to restore enzyme activity to a level sufficient to remove accumulated substrate from organ tissues, thereby preventing, stabilizing, or reversing the progressive decline in organ function before irreversible damage occurs.

Following intravenous infusion, agalsidase beta is rapidly cleared from bloodstream and is taken up by the lysosomes of parenchymal and endothelial cells, which they probably enter via mannose-6 phosphate, mannose, and asialoglycoprotein receptors.

1.1.3 Pharmacokinetics

Following intravenous administration of agalsidase beta to adults dosed at 0.3 mg, 1 mg, and 3 mg/kg of body weight, AUC values increased more than dose-proportionally due to decreased clearance, which indicated saturated clearance. The elimination half-life was not dose-dependent and ranged from 45 to 100 minutes.

Following intravenous administration of agalsidase beta to adults with an infusion time of approximately 300 minutes and dosed at 1 mg/kg/body weight, every two weeks, mean plasma C_{max} ranged from 2,000 to 3,500 ng/mL, while that the $AUC_{0-\infty}$ ranged from 370 to 780 mcg.min/mL. The mean volume of distribution at steady state ranged from 8.3-40.8 L, plasma clearance from 119-345 mL/min. and the mean elimination half-life from 80 to 120 minutes.

Beta agalsidase is a protein and is predicted to be metabolically degraded by peptic hydrolysis. Therefore, hepatic impairment is not expected to impact on the pharmacokinetics of agalsidase beta in a clinically significant manner. Renal clearance of agalsidase beta is considered a secondary clearance pathway.

1.1.4 Dosing Regimen and Administration

The dose to be used in this study on agalsidase beta is 1 mg/kg/body weight, administered as an intravenous infusion.

The rationale is as follows:

- The recommended dose of agalsidase beta comparator is 1 mg/kg of body weight, administered once every 2 weeks by intravenous infusion.
- It is the dose that did not cause adverse events in preclinical studies in animals, conducted on the same Biosidus S.A. molecule, which defines this dose as the NOAEL.
- It is the dose used in the biosimilar study conducted in Japan¹⁵.

The initial infusion rate should not exceed 0.25 mg/min (15 mg/h) to minimize the potential for infusion-related reactions. Once the volunteer's tolerance has been established, the infusion rate can be gradually increased for subsequent infusions.

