SPONSOR	Biosidus S.A. [name] [contact] [contact]
PRINCIPAL INVESTIGATOR	[name] [name] [contact]
CO – INVESTIGATOR	[name]
REGULATORY HEAD	[name]
SITE	Sanatorio Nuestra Señora del Pilar [name]
LABORATORIES	
 • Enzyme Activity Assessment: Biosidus Development Department - [name], Argentina - [contact] - [contact] • Immunogenicity Assessment: Biosidus Development Department - [name], Argentina - [contact] - [contact] • Pharmacokinetic Assessment: Shin Nippon Biomedical Laboratories, Ltd., [name], [contact]; [contact]
PRIMARY OBJECTIVE	Compare the pharmacokinetic behavior of Biosidus Agalsidase beta and Fabrazyme® (Genzyme) after administration by intravenous infusion of 1 mg/kg over a period of 5 hours of one of the following formulations: - Fabrazyme®, by Sanofi Genzyme (Reference Formulation, "R") - Agalsidase beta, biosimilar developed by Biosidus SA (Test Formulation, "T")

SECONDARY OBJECTIVE	Evaluation of enzyme activity, product safety, incidence of adverse events and tolerance. Evaluation of antibody occurrence.
STUDY DESIGN	Open, randomized, parallel-arms, balanced, single-dose, and sequential
DISCONTINUATION SCHEDULE	The sponsor and investigators may independently discontinue the study at any time at the sole possibility or occurrence of a serious adverse event or situation that could affect the volunteer's health.
NUMBER OF VOLUNTEERS	A total of 20 (twenty) male volunteers will initially be included. As it is a sequential design, if the statistical analysis on the first 20 volunteers does not demonstrate bioequivalence, an additional number of healthy volunteers to be determined will be included to verify the similarity criterion with adequate power.

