STUDY VISITS	
 • Visit I: Selection of volunteers, obtaining informed consent and completion of entrance exams. • Visit II: It will consist of a 24-h hospitalization for the administration of the R or T product, assigned according to the volunteer randomization. Sampling times for the investigational product pharmacokinetic quantification for each volunteer will be: pre-dose (0 h), 1 h, 3 h, 5 h, 5.5 h, 6 h, 7 h, 8 h, 10 h and 12 h. h from the beginning of the infusion. For the assessment of enzymatic activity, the following assessment times will be taken: pre-dose (0 h), 1 h, 3 h, 5 h, 5.5 h, 6 h, 7 h, 8 h, 10 h and 12 h. For the assessment of immunogenicity, the following evaluation times will be taken: pre-dose (0 h) and 12 h. • Visit III, IV, V and VI (telephone contact): The principal investigator or the delegated medical staff will contact the volunteer by telephone after Visit II to ask about medication tolerance and the presence of adverse events to the days 3, 7 and 14 respectively. • Visit VII (end of study visit): It will be carried out 35 days after Visit I, to evaluate the general clinical and biological status of volunteers. The same studies performed at the initial visit will be repeated. For the assessment of immunogenicity, samples will be taken to be evaluated at 35 days.
INVESTIGATIONAL PRODUCT/S DOSAGE AND ROUTE OF ADMINISTRATION	
A single dose of 1 mg/kg of agalsidase beta will be administered intravenously in an accurate strength to each volunteer for 5 h.
 
The following formulations will be used:
 
 • Sanofi Genzyme Fabrazyme® (Reference Formulation, "R") supplied as 35 mg and 5 mg lyophilized powder to be reconstituted for infusion. • Agalsidase beta, a biosimilar developed by Biosidus S.A. (Test Formulation, "T") supplied as 35 mg and 5 mg lyophilized powder to be reconstituted for infusion.
COMPARATIVE ASSESSMENT OF	From the results of the serum concentration of agalsidase beta, at the different sampling times, the following variables will be estimated:

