2 STUDY OBJECTIVES

Primary Objective

The objective of this trial is to compare the pharmacokinetic behavior after administration by intravenous infusion over a period of 5 hours of a single administration of 1 mg/kg

Biosidus Agalsidase beta (Test Formulation, "T") versus an intravenous infusion of Sanofi-Genzyme Fabrazyme® at the same strength (Reference Formulation, "R").

Secondary Objectives

Evaluate and compare the plasma enzyme activity of agalsidase beta, the eventual induction of anti-agalsidase beta antibodies and the occurrence and frequency of adverse effects and tolerance to the formulations studied.

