5.2 INCLUSION CRITERIA

- 1) Male subjects aged between 18 and 40 years.
- 2) Body mass index (BMI) between 19 and 25 kg/m²
- 3) Volunteers whose investigations (ECG, chest X-ray, blood and urine, PCR for COVID-19), performed prior to their inclusion and are within normal limits and/or without clinical significance at the investigator's discretion.
- 4) Subjects with systolic blood pressure higher than 110 mm Hg and lower than 139 mm Hg, a diastolic pressure higher than 70 mm Hg and lower than 89 mm Hg with a heart rate higher than 50 and lower than 90 beats per minute after being 5 minutes in a sitting position and then in a standing position (outliers included).
- 5) Volunteer being willing to participate in the study and who has signed the informed consent approved before the study initiation.

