6.2 MATERIAL PREPARATION AND LABELING

Medication used in the study will be provided by Biosidus S.A., in accordance with current regulations. Preparation for the medication used for each volunteer will be made by the principal investigator, or his designee, as follows.

Each volunteer will receive one (1) intravenous infusion in the arm. Vials will be labeled with a self-adhesive label where the study code and other information necessary for the label of the investigational product will be mentioned, in accordance with ANMAT Provision 6677/2010, as indicated in Annex 3. Reconstitution and dilution for each volunteer will be made based on his body weight.

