Annex 3: Storage and labeling

Each treatment unit corresponds to one bottle for intravenous administration of Biosidus Agalsidase or Sanofi Genzyme Fabrazyme® for a period of 5 hours.

Bottle label for each patient contains the following information: Protocol No: RD-BIO—AGA-01/03/21

Bottle N°:

Patient Initials: _____

Pacient N°: _____

Investigator's Name: [name]

Date of provision: _____

Lot N°:

Date of Expiration: November 30, 2021

Store between 2°C to 8°C, protect from heat, light and excessive moisture.

For exclusive use in clinical research. Keep out of reach of children.

Biosidus [name]

Note: Bottle N° 1 with 35 mg or Bottle N° 2 with 5 mg.

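### Above 75 kg, 1 mg/kg over a constant 5 h exceeds the 15 mg/h initial-rate limit, and the plan provides no step-up within its single infusion (minor)

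*Combined protocol and SAP*

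**What the plan says.** Section 1.1.4 sets the study dose at 1 mg/kg and then gives the protocol's only rate instruction: "The initial infusion rate should not exceed 0.25 mg/min (15 mg/h) to minimize the potential for infusion-related reactions". Once tolerance is established, "the infusion rate can be gradually increased for subsequent infusions".

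The duration is stated consistently and without adjustment for weight. The Protocol Summary has "after administration by intravenous infusion of 1 mg/kg over a period of 5 hours" under the primary objective and "will be administered intravenously in an accurate strength to each volunteer for 5 h" under dosage. Section 2 has "over a period of 5 hours of a single administration of 1 mg/kg", and Annex 3 has "Sanofi Genzyme Fabrazyme® for a period of 5 hours".

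Section 6.2 states: "Each volunteer will receive one (1) intravenous infusion in the arm". Section 6.4 confirms that each volunteer receives only one formulation, at Visit II.

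Section 5.2 requires "Body mass index (BMI) between 19 and 25" kg/m². No section limits body weight or total dose. Sections 4.4.1, 6.2 and 6.3, which govern the visit, preparation and dose, give no infusion rate, step-up rule or weight-dependent duration.

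**The concern.** Dose and duration together fix the average rate. In a heavy enough man that average is above the stated limit. The one sentence that permits a higher rate ties it to later infusions, and this trial has none. Staff treating such a man could run a constant rate above the limit, improvise a step-up, or prolong the infusion. The protocol does not say which.

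The limit is there to reduce infusion reactions in healthy men who gain nothing from treatment. Prolonging the infusion would also mean that the 5 h sample, which section 7.2 treats as the end-of-infusion activity sample, is drawn before the infusion has ended.

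**Working it through.** **Inputs.** Rate limit 0.25 mg/min, single dose of 1 mg/kg, duration 5 h, BMI 19-25 (section 1.1.4, Protocol Summary, section 5.2). Half-life 45-100 min and 80-120 min (section 1.1.3). Planning CV 0.15 (section 10). The documents give no heights or weights, so those are assumed below.

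**1. The plan's own figure.** 0.25 x 60 = 15 mg/h, as stated.

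**2. Threshold.** A man of W kg receives W mg in 5 h, so a constant infusion runs at W/5 mg/h. W/5 = 15 gives W = 75 kg.

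| Weight | Constant rate W/5 | Over 15 mg/h | Duration needed at 15 mg/h (W/15) |
|---|---|---|---|
| 75 kg | 15.0 mg/h | 0% | 5.0 h |
| 81 kg | 16.2 mg/h | 8% | 5.4 h |
| 85 kg | 17.0 mg/h | 13% | 5.67 h |
| 90 kg | 18.0 mg/h | 20% | 6.0 h |

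**3. Are such men eligible?** Height at which 75 kg is reached = sqrt(75/BMI): 1.73 m at BMI 25, 1.77 m at BMI 24, 1.81 m at BMI 23. So yes.

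**4. How many?** Assumption: height normal with mean 1.70-1.77 m and SD 0.07 m; BMI on 19-25, either uniform or triangular with mode 22 or 24. By simulation:
- Uniform BMI: 7% (mean 1.70 m) to 22% (mean 1.77 m) exceed 75 kg. The median weight of those men is 77.5-78.8 kg, so a constant rate of 15.5-15.8 mg/h, or 3-5% over.
- All three shapes: about 4-29%, that is 0.04 x 20 = 0.8 to 0.29 x 20 = 5.8 of 20 volunteers.
- Uniform BMI: 1-7% exceed 81 kg and 0.2-2% exceed 85 kg, so the larger excesses in the table are uncommon.

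**5. Effect of a step-up on the measurements.** Take 15 mg/h for 1 h, then (W - 15)/4 mg/h for 4 h. In a one-compartment linear model with k = ln 2 / half-life (in hours), the level at 5 h is proportional to:
- constant rate: (W/5)(1 - e^(-5k));
- step-up: 15(1 - e^(-k))e^(-4k) + ((W - 15)/4)(1 - e^(-4k)).

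Example, 85 kg and 80 min: k = 0.520. Constant: 17 x 0.9257 = 15.74. Step-up: 15 x 0.4054 x 0.125 + 17.5 x 0.875 = 0.76 + 15.31 = 16.07. Ratio 1.021.

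| Weight | Later rate | Level at 5 h against constant rate (half-life 120 to 45 min) |
|---|---|---|
| 77.5 kg | 15.6 mg/h | +0.5% to +0.8% |
| 79 kg | 16.0 mg/h | +0.7% to +1.2% |
| 85 kg | 17.5 mg/h | +1.6% to +2.7% |
| 90 kg | 18.75 mg/h | +2.3% to +3.9% |

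AUC from 0 to 12 h changes by about 0.1% or less.

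**6. Effect on the test/reference comparison.** The rule depends on weight, not formulation, and section 4.1 intends balance on anthropometric variables. If one arm of 10 nevertheless had three more men at 79 kg, its mean log end-of-infusion level would shift by about 3/10 x 1.2% = 0.4%. The added spread is also trivial: the SD of the log change over all volunteers is at most about 0.0075, and sqrt(exp(ln(1 + 0.15²) + 0.0075²) - 1) = 0.1502 against 0.15.

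**The case against.** The best defense is linguistic. An initial rate ordinarily means a starting rate, the wording is advisory, and the phrase about later infusions looks like repeat-dose text carried into a background chapter. The operative dosing text is consistent and implies W/5 mg/h. Pump instructions may also sit in a package insert or pharmacy document that is not included here.

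Part of this stands. Read as a starting rate, the limit can be met at any weight, so the instructions are not impossible to follow. But that reading needs a step-up within the infusion, and the protocol gives none; a constant 5 h infusion still starts above the limit in these men. The rate text also speaks of the volunteer's tolerance, so it addresses trial participants. If it was carried over, that is a reason to correct it.

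Two stronger inferences are tempting and not supported:

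- A reader might infer a material safety hazard, since section 1.1.8 reports infusion reactions in 67% of patients. That figure is from patients. Section 1.1.6 expects little or no antibody response in these volunteers, and section 1.1.3 describes 1 mg/kg over about 300 minutes in adults with no weight exception. Sections 4.4.1 and 4.5 provide staggered admission, continuous clinical evaluation and vital signs before each draw. The added risk from a rate 3-5% higher cannot be estimated from the documents.
- A reader might infer that the pharmacokinetic comparison is compromised. If 5 h is kept, step 6 shows that it is not.

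**Conclusion.** The rate limit and the fixed duration conflict as written for men above 75 kg, and the only stated route out is unavailable in a single-infusion trial. This is wrong as written, but minor: an unclear safety instruction, not a weakness in the analysis.

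The 75 kg threshold is exact, given that dose and limit are both in labeled milligrams. The rest rests on assumptions. The share affected (about 4-29%) depends on assumed heights and BMI shapes. The typical excess of 3-5% holds under the same assumptions. The concentration changes come from a linear model, whereas section 1.1.3 reports saturable clearance, so they are approximate. The safety gain from correcting the text is probably very small and cannot be quantified.

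**What to change.** Amend section 1.1.4 and the dosing text in the Protocol Summary, section 4.4.1 and section 6.3 to one rule:

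- 5 h for every volunteer.
- Start at no more than 15 mg/h.
- For men above 75 kg who tolerate an initial period, raise the rate once within the same infusion so that it finishes at 5 h; for example, (W - 15)/4 mg/h after 1 h.
- The sponsor's clinicians set the initial period and the maximum rate. The documents give no basis for either, and the 1 h above is only an illustration.
- Remove the restriction of rate increases to later infusions.
- If an infusion is slowed or prolonged, take the end-of-infusion sample at its actual end.

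The cost is a few sentences, with no extra volunteers, samples or visits. There is one real downside: the later rate is slightly above the constant rate (17.5 against 17.0 mg/h at 85 kg), which produces the small rise in end-of-infusion level shown in step 5. Capping the whole infusion at 15 mg/h would avoid this, but it lengthens the infusion to W/15 h in heavier men and moves the end of infusion away from the 5 h sample.

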1.1.5 Contraindications

Life-threatening hypersensitivity (anaphylactic reaction) to the drug substance or to any of the inactive ingredients.

1.1.6 Warnings

Immunogenicity:

As agalsidase beta (recombinant human α -galactosidase A or r-haGAL) is a recombinant protein, development of IgG antibodies is expected to occur in patients with little or no residual enzyme activity. In studies that resulted in the approval of the reference medicine, most patients developed IgG antibodies to r-haGAL, mainly within 3 months of the first drug infusion. Over time, most seropositive patients in clinical trials showed a decreasing trend in titers (based on a \geq 4-fold reduction in titers from peak measurement to the last measurement) (40% patients) or they showed tolerance (no detectable antibody was confirmed by 2 consecutive radioimmune precipitation assays (RIPA)) (14% patients) or showed a plateau (35% patients). Healthy volunteers participating in this study, whose enzyme activity is normal, are expected to have little or no antibody response to agalsidase beta administration.

Infusion-Related Reactions:

Patients with antibodies to recombinant agalsidase beta (recombinant human α -galactosidase A or r-haGAL) are more likely to experience infusion-related reactions (IRRs) defined as any related adverse effect occurring on the day of the infusion. These patients should be treated with caution when re-administering agalsidase beta. Antibody status in patients with Fabry disease and on treatment should be monitored regularly.

Hypersensitivity

Allergic hypersensitivity reactions may occur, as with any other protein medication for intravenous administration.

If serious allergic or anaphylactic reactions occur, agalsidase beta administration should be discontinued immediately and appropriate treatment should be initiated. Current standards for emergency medical treatment of this situation will be followed.

Patients with Advanced Kidney Disease

The renal effect of agalsidase beta treatment may be limited in patients with advanced kidney disease.

1.1.7 Interactions

Biosidus has not conducted any *in vitro* metabolism or drug interaction studies. A literature search did not provide data on this type of study either. Given its metabolism, cytochrome P450-mediated drug interactions are unlikely to occur with agalsidase beta. It should not be administered with chloroquine, hydroxychloroquine, amiodarone, or aminoglycosides (amikacin, streptomycin, gentamicin, or tobramycin), due to the theoretical risk of inhibition of α -galactosidase A activity.

1.1.8 Adverse Reactions

Safety Profile Summary

As agalsidase beta (r-haGAL) is a recombinant protein, development of IgG antibodies is expected to occur in patients with little or no residual enzyme activity.

Patients with antibodies to r-haGAL are more likely to experience infusion-related reactions. Cases of reactions suggestive of immediate hypersensitivity (type I) have been reported in a small number of patients.

Chills, pyrexia, feeling cold, nausea, vomiting, headache and paraesthesia are included as very common adverse reactions. 67% of patients experienced at least one infusion-related reaction. In some cases anaphylactoid reactions have been reported. Treatment considered for anaphylactic reactions is adrenaline, corticosteroids (dexamethasone/hydrocortisone) and antihistamine (diphenhydramine).

1.1.9 Pregnancy and Breastfeeding

There are no sufficient data from the use of agalsidase beta in pregnant women.

Studies in animals do not indicate direct or indirect harmful effects on embryonic/fetal development.

Agalsidase beta should not be used during pregnancy unless clearly necessary.

Agalsidase beta may be excreted in breast milk. As there are no data on the effects on newborns exposed to the drug through breast milk, breastfeeding discontinuation is recommended when initiating treatment.

1.1.10 Overdose

Clinical studies with agalsidase beta have used up to 3 mg/kg of body weight.

1.1.11 Storage Conditions

Store in the refrigerator at a temperature between 2 °C and 8 °C in its original container.

Reconstituted solution should not be stored and should be diluted quickly. Diluted solution may be kept for up to 24 hours at a temperature between 2 °C and 8 °C.

2 STUDY OBJECTIVES

Primary Objective

The objective of this trial is to compare the pharmacokinetic behavior after administration by intravenous infusion over a period of 5 hours of a single administration of 1 mg/kg

Biosidus Agalsidase beta (Test Formulation, "T") versus an intravenous infusion of Sanofi-Genzyme Fabrazyme® at the same strength (Reference Formulation, "R").

Secondary Objectives

Evaluate and compare the plasma enzyme activity of agalsidase beta, the eventual induction of anti-agalsidase beta antibodies and the occurrence and frequency of adverse effects and tolerance to the formulations studied.

